7.3.4. UFS-QoL Score

The change from baseline in the UFS-QoL Bleeding and Pelvic Discomfort (BPD) Scale score, UFS-QoL Symptom Severity Scale score, UFS-QoL Revised Activities Scale, UFS-QoL subscale scores, and total scores will be summarized as specified in [Section 7.1.2](#). In addition, the proportion of responders as measured by the BPD Scale score and Revised Activities Scale will be summarized, as described below.

Calculation of UFS-QoL Symptom Severity Scale Score

To calculate the Symptom Severity Scale score, a summed score is created for the items listed below and then the formula below the table is used to transform raw scores to a normalized score with a range of possible values from 0 to 100. This provides Symptom Severity Scale scores, where higher scores are indicative of greater symptom severity and lower scores indicate lower symptom severity.

Scale	Sum Item Values	Lowest and Highest Possible Raw Scores	Possible Raw Score Range
Symptom Severity	Sum 1 – 8	8, 40	32

Formula for Transformation of Symptom Severity Raw Scores ONLY:

$$\text{Transformed Score} = \frac{[(\text{Actual raw score} - \text{lowest possible raw score}) / (\text{Possible raw score range})] * 100}$$

Calculation of UFS-QoL Bleeding and Pelvic Discomfort Scale Score

The UFS-QoL BPD Scale has been derived from the UFS-QoL Symptoms Scale; the derivation and validation of this new scale can be found in the MVT-601-3001/3002 SAP. The new scale consists of the following three symptoms proximal to uterine fibroids:

- Heavy bleeding during your menstrual period (Q1)
- Passing blood clots during your menstrual period (Q2)
- Feeling tightness or pressure in your pelvic area (Q5)

To calculate the score for the BPD Scale, a summed score of the items listed below is created and then the formula below the table is used to transform the raw score to a normalized score. This provides BPD Scale scores, where higher score values are indicative of greater symptom severity and lower scores will indicate minimal symptom severity (high scores = bad).

Sub-Scale	Sum Item Values	Lowest and Highest Possible Raw Scores	Possible Raw Score Range
Q1, Q2 and Q5	Sum 1,2,5	3, 15	12

Formula for Transformation of BPD Raw Scores ONLY:

$$\text{Transformed Score} = \left[\frac{(\text{Actual raw score} - \text{lowest possible raw score})}{(\text{Possible raw score range})} \right] * 100$$

On the basis of transformed score for BPD Scale, change from Baseline in the transformed score for BPD Scale at Week 52 will be defined as a secondary endpoint. The proportion of patients who are responders (defined as meeting a meaningful change threshold from Baseline in the BPD Scale) at Week 52 on the transformed score for the BPD Scale will be summarized for each treatment group. The proposed responder threshold is a 20-point change. Details in the determination of the meaningful change in the BPD Scale can be found in the MVT-601-3001/3002 SAP Appendix 4.

As a descriptive assessment on robustness of the responder analysis, a plot of the cumulative distribution function (CDF) will be provided for each treatment group to display the change from Baseline to Week 52 in the transformed score for BPD Scale on the x-axis and cumulative percentage of patients experiencing up to that change on the y-axis.

Calculation of Other UFS-QoL Scale Scores and UFS-QoL Total Score

For the other UFS-QoL scales (concern, activities, revised activities, energy/mood, control, self-conscious, and sexual function), a summed score of the items listed below is created for each individual scale. To calculate the UFS-QoL total score, the values for each individual scale are summed. Using the formula below the table, all raw scores are transformed to normalized scores. Higher scores are indicative of better health-related quality of life (high = good).

For endpoints evaluating a single question, the raw score is used in the analysis. The activity and revised activity domain scores will be summarized by treatment group.

Scale	Sum Item Values	Lowest and Highest Possible Raw Scores	Possible Raw Score Range
Concern	9+15+22+28+32	5, 25	20
Activities	10+11+13+19+20+27+29	7, 35	28
Revised activities	11+13+19+20+27	5,25	20
Energy/mood	12+17+23+24+25+31+35	7, 35	28
Control	14+16+26+30+34	5, 25	20
Self-conscious	18+21+33	3, 15	12
Sexual function	36+37	2, 10	8
HRQL TOTAL	Sum of 6 Subscale Scores^a	29, 145	116

Abbreviations: HRQL, health-related quality of life.

^a HRQL Total includes following scales: concern, activities, energy/mood, control, self-conscious, and sexual function.

Formula for Transformation of Raw Scores of Other Scale Scores ONLY:

$$\text{Transformed Score} = [(\text{Highest possible score} - \text{Actual raw score}) / (\text{Possible raw score range})] * 100$$

For revised activities, the proportion of patients who are responders (defined as meeting a meaningful change from Baseline in the revised activity score) at Week 52 will be analyzed similarly to that for the change in BPD Scale score for each treatment group. The proposed responder threshold is a 20-point increase. Details of the determination of the meaningful change in the Revised Activities Scale score can be found in the MVT-601-3001/3002 SAP Appendix 5.

Missing Items

For any scale analyses, if < 50% of the scale items are missing, the scale should be retained using the mean scale score of the items present. If ≥ 50% of the items are missing, no scale score should be calculated; the subscale score will be considered missing.

7.3.5. Change from Baseline to Week 52 in Uterine Volume and Uterine Fibroid Volume

For evaluating percent change from Baseline in uterine fibroid volume and uterine volume that are measured at Week 52, an analysis of covariance (ANCOVA) model will be used to calculate LS means and 95% CI, with randomization stratification factors and Baseline value as covariates. This model will be run separately for each treatment group.

7.3.6. Menorrhagia Impact Questionnaire

The Menorrhagia Impact Questionnaire results at each visit will be displayed in a by-patient listing.

7.4. Exploratory Efficacy Endpoints

The following exploratory endpoints will be assessed:

- Change from Baseline to Week 52 in the EQ-5D-5L Scale score
- Change from Baseline to Week 52 in EQ-5D-5L visual analogue score (VAS).

7.4.1. Exploratory Efficacy Analyses

The score for each dimension of the EQ-5D-5L Scale (mobility, self-care, usual activities, pain/discomfort, and anxiety/depression) will be summarized by visit (baseline, Week 24, Week 52). The change from baseline at Week 24 and Week 52 will be summarized by amount of improvement (1-4 categories), amount of deterioration (1-4 categories), or no change. The VAS will be summarized at each visit and the change from baseline will be summarized at Week 24 and 52 as specified previously for continuous endpoints.

8. PHARMACODYNAMIC ANALYSES

Serum pharmacodynamic data for the extension study consists of serum E2 trough concentrations. This data will be listed and summarized using descriptive statistics (including raw and change from Baseline) by parent study treatment group, and visit. The number and percentage of patients with individual E2 concentration values < 10 pg/mL, 10 to < 20 pg/mL, 20 to < 50 pg/mL, 50 to < 70 pg/mL and ≥ 70 pg/mL will be summarized by parent study treatment group and visit. E2 concentration values below the limit of quantification will be set to half of the lower limit of quantification. Boxplots of E2 concentration values over time, including visits in both the parent study and extension study, will be plotted.

9. SAFETY ANALYSES

Unless otherwise specified, safety analyses will be conducted using the Extension Safety population according to the actual treatment received by the patients in the parent study.

9.1. Adverse Events

Adverse events will be collected from the time of the first dose of open-label study drug through the safety follow up visit approximately 30 days after the last dose of open-label study drug (the end of extension treatment period), or the date of initiation of another investigational agent or hormonal therapy or surgical intervention or entering the MVT-601-035 study, whichever occurs first. Serious adverse events reported to the investigator after the safety reporting period should be reported to the sponsor if the investigator assesses the event as related to study drug.

The severity of all treatment-emergent adverse events will be evaluated by the investigator based on the National Cancer Institute's Common Terminology Criteria for Adverse Events (CTCAE) and will be coded to preferred term and system organ class using MedDRA 22.0 or higher.

A treatment-emergent adverse event is defined as any adverse event that occurs after administration of the first dose of parent study drug.

Adverse event summaries will be based on treatment-emergent adverse events in the parent and extension studies, unless otherwise specified. All adverse events in the parent and extension studies will be listed in by-patient listings.

The following tabular summaries that include the number and percentage of patients will be provided:

- Overview of adverse events;
- All adverse events;
 - By SOC and PT;
 - By decreasing frequency of PT;
 - By SOC, PT, and maximum severity;
 - Study drug-related per investigator by SOC and PT;
 - By time to onset, SOC and PT;
- Grade 3 or above adverse events;
 - By SOC and PT;
 - By decreasing frequency of PT;
 - Study drug-related per investigator by SOC and PT;
- Grade 2 or above adverse events;
 - By SOC and PT;
 - By decreasing frequency of PT;
 - By SOC, PT, and maximum severity;

- Study drug-related per investigator by SOC and PT;
- Adverse events leading to study drug withdrawal;
 - By SOC and PT;
 - By decreasing frequency of PT;
- Adverse events leading to dose interruption;
 - By SOC and PT;
 - By decreasing frequency of PT;
- Adverse events resulting in fatal outcome;
 - By decreasing frequency of PT;
- Serious adverse events;
 - By SOC and PT;
 - By decreasing frequency of PT;
 - By SOC, PT, and maximum severity;
 - By SOC, PT, and relationship to study drug;
- Adverse events of clinical interest (ALT or AST $\geq 3 \times$ ULN);
 - By SOC, PT, and maximum severity;
 - By decreasing frequency of PT.
- Adverse events with first onset during the extension study;
 - By SOC and PT;
 - By decreasing frequency of PT;

Additionally, adverse event categories defined in [Table 12](#) will be summarized by decreasing frequency of PT.

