5.9.3. Prohibited Non-Drug Therapies

Surgical and other interventional treatment of uterine fibroids is prohibited from the Week 24/Baseline visit until the patient's final study visit unless urgently needed for patient safety.

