7.2.1. Adverse Event Reporting Period

Adverse events and serious adverse events will be collected under this extension study protocol from the administration of the first dose of extension study drug until the Follow-up visit approximately 30 days after the last dose of study drug or the date of initiation of another investigational agent or hormonal therapy affecting the hypothalamic-pituitary-gonadal axis or surgical intervention for uterine fibroids, whichever occurs first, as also specified in the study Schedule of Activities (Section 1.1). Serious adverse events reported to the investigator after the safety reporting period should be reported to the sponsor if the investigator assesses the event as related to the study drug treatment.

Reporting instructions for serious adverse events are provided in Section 7.6.

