9.5. Safety Analyses

Safety assessments will include treatment-emergent adverse events, vital signs, physical examinations, clinical laboratory tests, and 12-lead ECGs.

The treatment-emergent period will be defined as the period of time from the first dose date of study drug in the parent study through approximately 30 days after the last dose of study drug, or the date of initiation of another investigational agent or hormonal therapy affecting the hypothalamic-pituitary-gonadal axis or surgical intervention for uterine fibroids, whichever occurs first. Safety will be assessed through summaries of adverse events, the frequency of treatment discontinuations due to adverse events, laboratory evaluations, and bone densitometry results.

The severity of all adverse events is to be evaluated by the investigator based on the National Cancer Institute's CTCAE. All adverse events will be coded to preferred term and system organ class using MedDRA 20.0 or higher. The incidence of adverse events will be presented by MedDRA system organ class and preferred term, relationship to study drug treatment, and severity. A patient reporting the same adverse event more than once is counted once, and at the maximum severity or strongest relationship to study drug treatment when calculating incidence.

Laboratory data consist of chemistry, hematology, and hormonal tests. Only data collected by the central laboratory will be used to do the analyses. The National Cancer Institute CTCAE, will be used to categorize toxicity grade for the laboratory parameters. Shift tables will be provided for each gradable parameter to summarize baseline toxicity grade versus post-baseline toxicity grade. For laboratory parameters that are not gradable by the CTCAE, a shift table based upon the normal range (low, normal, and high) will be provided for each parameter to summarize the parent study Baseline versus post-baseline results. All data will be listed and summarized by visit. The change from parent study Baseline to each post-baseline study visit will be presented by parent study treatment group for each laboratory test.

For vital signs parameters, including temperature, all data will be listed and summarized by visit. The change from parent study Baseline to each post-baseline study visit will be presented by parent study treatment group for each parameter.

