5.2. Protocol Deviations

Protocol deviations that occurred during the extension study will be categorized as important or minor per the protocol deviation plan. Important protocol deviations will include, but will not be limited to, the following categories:

- Patient treated with open-label study drug who did not satisfy key entry criteria;
- Patient treated with open-label study drug who met withdrawal criteria during the study but was not withdrawn;
- Patient treated with open-label study drug who received a prohibited concomitant medication that met criteria for an important protocol deviation.

Important protocol deviations will be summarized by deviation category for all patients in the Extension Safety population. A patient listing of all important protocol deviations will be provided.

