9.1.8. Exposure-adjusted Adverse Events

Adverse events by time to onset and an exposure-adjusted adverse event analysis will be provided. The exposure-adjusted adverse event rate will be summarized by system organ class and preferred term for each parent study treatment group, where the exposure-adjusted adverse event rate is calculated as number of patients with a particular adverse event by total exposure-time among patients at risk of an initial occurrence of the event. Exposure-time is derived as exposure to any study drug throughout the parent and extension study.

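### The adverse-event cut-off triggers are not confined to the time after the last dose, and the collection window, treatment-emergent period and exposure time do not match

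*SAP*

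**What the plan says.** **Collection.** SAP 9.1 runs collection from the first open-label dose to the follow-up visit about 30 days after the last dose, "or the date of initiation of another investigational agent or hormonal therapy or surgical intervention or entering the MVT-601-035 study, whichever occurs first". Protocol 7.2.1 has the same form, with narrower triggers: "hormonal therapy affecting the hypothalamic-pituitary-gonadal axis or surgical intervention for uterine fibroids, whichever occurs first, as also specified in the study Schedule of Activities".

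**Treatment-emergent period.** Protocol 9.5 starts it at the first parent-study dose and ends it about 30 days after the last dose or at another investigational agent, "hormonal therapy affecting the hypothalamic-pituitary-gonadal axis or surgical intervention for uterine fibroids, whichever occurs first. Safety will be assessed through summaries". SAP 9.1 gives only a start: "A treatment-emergent adverse event is defined as any adverse event that occurs after administration of the first dose of parent study drug". It bases its summaries on all such events in both studies.

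**Exposure and denominators.** SAP 9.1.8 states: "Exposure-time is derived as exposure to any study drug throughout the parent and extension study". SAP 4.3.5 runs treatment duration to the last extension dose. SAP 4.1 takes safety percentages over everyone in the analysis population of the group.

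**Trigger events during treatment.** Protocol 5.9.3 prohibits fibroid surgery "unless urgently needed for patient safety". Protocol Table 3 prohibits sex hormones. Among its important deviations, SAP 5.2 foresees this category: "Patient treated with open-label study drug who received a prohibited concomitant medication that met criteria for an important protocol deviation". Protocol 4.5 names neither surgery nor hormone use as a removal event, although its non-compliance item leaves room for judgement.

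**The concern.** In all three places the rule takes the earliest of several dates, and some of those dates can fall during treatment. Suppose a woman has urgent fibroid surgery mid-extension and continues study drug. Under Protocol 7.2.1 her adverse-event record closes on the day of surgery. After that, the general rule asks only for serious events that the investigator judges related. The definition of unrelated in Protocol 7.3 includes events for which another drug or the underlying disease is a plausible explanation, so a post-operative event could readily be classed as unrelated and go unreported.

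Her later weeks on drug still count in the exposure-adjusted rate, and she stays in the denominator of every crude percentage. The numerator can lose events and the denominator cannot, so the error runs in one direction. Adverse-event incidence is one of the trial's two safety endpoints. Sites could also differ: one working from the Schedule would record events that one working from 7.2.1 would not.

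**Working it through.** The plan states no figure for this point, so there is none to reproduce. The check compares the texts and then sizes the effect.

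**Step 1. Texts side by side**

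| Place | End point | Limited to after last dose? | Qualifiers on hormone and surgery? |
|---|---|---|---|
| Protocol 7.2.1 (collection) | Follow-up visit or first trigger | No | Yes |
| Protocol 9.5 (treatment-emergent) | About 30 days after last dose or first trigger | No | Yes |
| SAP 9.1 (collection) | Follow-up visit or first trigger | No | No |
| SAP 9.1 (treatment-emergent) | None given | n/a | n/a |
| SAP Tables 2, 5 and 6, footnotes | Safety follow-up window only | Yes | Yes |
| SAP Table 3, note (bone density) | First trigger | No | Yes |
| Protocol Schedule of Activities | Every visit; footnote y gives a start and no end | n/a | n/a |

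Four things follow.

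- Protocol 7.2.1 says that the Schedule specifies the same period, but the Schedule contains no such cut-off.
- An on-drug event recorded after fibroid surgery is treatment-emergent under SAP 9.1 and not under Protocol 9.5.
- SAP 4.3.10 compares partially dated events with the end of the treatment-emergent period, which SAP 9.1 never defines.
- The footnotes to SAP Tables 2, 5 and 6 show that wording confined to follow-up was available.

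**Step 2. Loss for one affected woman**

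If a trigger occurs at Week w and dosing continues to Week 52, the exposure counted without collection is 52 − w weeks.

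- w = 28: 24 weeks; 24/52 = 46.2%
- w = 38: 14 weeks; 14/52 = 26.9%
- w = 48: 4 weeks; 4/52 = 7.7%

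**Step 3. Effect on a group's 52-week rate**

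Let f be the share of women affected. The documents do not give it; I assume 1% and 5%. For orientation, that would be 6 to 30 of the planned 600 women. With a low, constant event rate that is equal in all women, and every event after the trigger lost:

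reported rate / true rate = [(1 − f) × 52 + f × w] / 52, so the relative understatement is f × (52 − w) / 52.

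| f | w = 28 | w = 38 | w = 48 |
|---|---|---|---|
| 1% | 0.01 × 24/52 = 0.46% | 0.01 × 14/52 = 0.27% | 0.01 × 4/52 = 0.08% |
| 5% | 0.05 × 24/52 = 2.31% | 0.05 × 14/52 = 1.35% | 0.05 × 4/52 = 0.38% |

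The range is about 0.1% to 2.3%. At f = 10% and w = 28 it would be 0.10 × 24/52 = 4.6%. Two simplifications pull in opposite directions: some events after the trigger are still captured, which shrinks the effect, and affected women may have more events than others, which enlarges it.

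**Step 4. After the repair**

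If the triggers act only after the last dose, no exposure week is without collection and the mismatch is zero.

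**The case against.** The best defence is that the triggers were meant only to shorten follow-up after treatment. Protocol 6.3 brings the Follow-up visit forward for nearly the same triggers, in women who have completed or withdrawn. The footnotes to SAP Tables 2, 5 and 6 attach the triggers to a window that opens 7 days after the last dose. Protocol 6.2 and Table 6 also call for adverse-event recording at each visit. This reading is plausible and may well be the intention. It is not what 7.2.1, 9.5 or SAP 9.1 say, however, and the note to SAP Table 3 applies the same triggers to bone density with no post-dose limit.

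The defence also limits the consequence, and these parts stand:

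- Fibroid surgery is prohibited unless urgent, and sex hormones are prohibited. SAP 7.2.4 foresees withdrawal for fibroid surgery. Loss requires a woman who has the trigger event and continues dosing.
- Related serious events are still reported, and SAP 9.1.3 includes deaths. ALT or AST of at least 3 × ULN must be reported throughout treatment and follow-up (Protocol 7.5). Overdose and pregnancy have their own reporting rules (7.7, 7.8).
- Non-serious heavy menstrual bleeding is not an adverse event under Protocol 7.1.1, so its absence is not a loss.
- The study is descriptive, with no formal test that a small understatement could overturn.

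A reader might infer from the dropped qualifiers that any operation, or any hormone such as thyroid replacement, closes a woman's record. The documents do not support that. Sites collect under the protocol, which keeps both qualifiers, and the open-ended SAP definition counts whatever is recorded.

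**Conclusion.** The point holds as an inconsistency in the written rules with a small, one-directional effect. Three things are established from the text: the triggers are not confined to the time after the last dose, SAP 9.1 drops both protocol qualifiers, and exposure time is not cut to match collection. In addition, the Schedule lacks the cut-off that 7.2.1 attributes to it, and the protocol and SAP treatment-emergent periods disagree.

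On the protocol's wording, what can be lost is non-serious events and serious events judged unrelated, with onset after fibroid surgery or a reproductive-axis hormone, in women who stay on drug. The same holds for the start of another investigational agent. The understatement of the 52-week rate is about 0.1% to 2.3% if 1% to 5% of women are affected between Weeks 28 and 48. That share is an assumption, and the true number is probably small.

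A reader might go further and conclude that the safety endpoint is materially biased, or that thromboembolic events disappear. The documents do not support this. Related serious events and deaths remain captured, and the effect on a whole group is modest even when every event after the trigger is taken as lost. The change is still worth making, because following the stated rule would discard on-drug safety data and the remedy is a few words.

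**What to change.** 1. In Protocol 7.2.1 and 9.5 and SAP 9.1, state that all adverse events from first to last dose are collected and counted as treatment-emergent whatever other therapy is given, and that the triggers shorten only the follow-up after the last dose.
2. In SAP 9.1, restore the two qualifiers: hormonal therapy acting on the hypothalamic-pituitary-gonadal axis, and surgery for fibroids.
3. Define the end of the treatment-emergent period once, and use that definition in SAP 9.1, SAP 4.3.10 and Protocol 9.5. Align the statement in 7.2.1 about the Schedule with what the Schedule contains.
4. Flag on-drug events with onset after such therapy or surgery, so that they can be listed or set aside in a sensitivity summary.

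Truncating exposure time at the trigger would also remove the mismatch, but it would give up on-drug safety observation.

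The cost is wording in two protocol sections and two SAP sections, plus one flag variable. A few events confounded by surgery or another hormone will appear in the adverse-event tables, where the flag identifies them. Nothing here bears on whether a woman should continue study drug after such an event.
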